3 RISK/BENEFIT ASSESSMENT

3.1.1 Known Potential Risks

No major side effects were noted from previous topical studies. Minor side effects from topical and oral CBD studies include nausea, diarrhea, fatigue, change in appetite, and weight gain/loss (3). Exogenous CBD may affect the metabolism of Coumadin and other drugs based on the P450 metabolism. Another theoretical risk is contact dermatitis.

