5 STUDY DESIGN

5.1 Overall Design

The study design will be a double-blind randomized controlled trial with crossover. Treatment will be blinded to the subjects and investigators. Patients will be randomly

assigned two (2) weeks of the case or control topical cream and then crossover to the other cream for two (2) more weeks. Patients will apply the cream at their thumb basal joint twice daily for one (1) hour. The subjects will be advised to observe for physiologic changes, skin changes, or other adverse effects. If mild to severe drug-related adverse events are noticed, the creams will be removed immediately and appropriate care and observation will be taken. Each condition will last for two (2) weeks and then subjects will be contacted by the study coordinator to facilitate crossover into the other condition. This study will last one year from the beginning of subject recruitment to data analysis. Subjects will be enrolled in this study for approximately six (6) weeks from Screening until the final Study Visit.

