6.2 Exclusion Criteria

An individual who meets any of the following criteria will be excluded from participation in this study:

1. Subject does not speak English.
2. Subject is blind.
3. Severe cardiac, pulmonary, liver and /or renal disease.
4. Coumadin use at time of screening.
5. History of mental illness.
6. Subjects who are incarcerated.
7. History of drug or substance abuse.
8. Pre-existing CBD or hemp based product usage.
9. Subject has had a corticosteroid injection \leq 3 months prior.
10. Subject has had prior surgery for osteoarthritis treatment.
11. Females who are pregnant, nursing or planning a pregnancy; females of childbearing potential who are unwilling or unable to use an acceptable method of contraception as outlined in this protocol from Screening to the first dose of study medication and for 30 days after the last dose of study medication. Standard acceptable methods include abstinence or the use of a highly effective method of contraception, including; hormonal contraception, diaphragm, cervical cap, vaginal sponge, condom with spermicide, vasectomy, intrauterine device.
12. Any skin disease or condition, including eczema, psoriasis, melanoma, acne or contact dermatitis, scarring, imperfections, lesions, tattoos or discoloration that may affect treatment application, application site assessments, or affect absorption of the study drug.
13. Subjects with ALT/AST >3 times the upper limit of normal at screening.
14. Subjects with history of or active depression or suicide ideation based on Columbia-Suicide Severity Rating Scale (C-SSRS).

15. Subjects taking prescription or non-prescription medication which are substrates of CYP3A4 (Itraconazole, Ketoconazole, Azamulin, Troleandomycin, Verapamil, John's wart, Phenobarbital), CYP2C19 (Nootkatone, Ticlopidine, Rifampin, Omeprazole), CYP2C8 (Montelukast, Quercetin, Phenelzine, Rifampin, Clopidogrel), CYP2C9 (Sulfaphenazole, Tienilic acid, Carbamazepine, Apalutamide, Fluconazole, Celecoxib), CYP1A2 (alpha-Naphthoflavone, Furaflavine, Phenytoin, Rifampin, Ritonavir, smoking, Teriflunomide, Ciprofloxacin, oral contraceptives, Alloprinol) and CYP2B6 (Sertraline, Phencyclidine, Thiotepa, Ticlopidine, Carbamazepine, Efavirene, Rifampin, Bupropion) within 14 days of the study procedure.

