7 STUDY INTERVENTION

7.1 Description of Study Intervention(s)

Product with description, all names, dosage form	Potency	Investigational or Standard of Care (SOC)	Packaging/Appearance	Manufacturer	Storage Conditions
Case – 99.99% pure cannabidiol (CBD) with 100% Pure USDA Organic Shea Butter	6.2 mg/mL	Investigational	Placed within 10mL syringe labeled with approved institutional labeling for research use only.	Eco-X, Inc, Grand Junction, CO (CBD) Mary Taylor Naturals, LLC, Fort Myers, FL (Shea Butter)	Room Temperature
Control – 100% Pure USDA Organic Shea Butter	N/A	Investigational	Placed within 10mL syringe labeled with approved institutional labeling for research use only.	Mary Taylor Naturals, LLC, Fort Myers, FL	Room Temperature

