9.2 Safety Assessments

Medical History: Relevant medical history, including history of mental illness, drug or substance abuse, history of hemp-based product usage and other pertinent history will be recorded in the case report form.

Laboratory Testing: At baseline and Study Day 35, blood draws will be performed on all subjects at the UVA Medical Laboratory. The following tests will be ordered and monitored for clinical abnormalities:

- CBC
- Basic metabolic panel (i.e., BUN, creatinine, CO₂, Cl, K, Na, and glucose)
- Hepatic function testing (i.e., serum transaminases [ALT/AST], total bilirubin, and alkaline phosphatase)
- Pregnancy Testing (if applicable) (Screening)
- Urine Pregnancy Test (if applicable) (Screening and Day 0 before dosing)

Daily Skin Monitoring: Subjects will be asked to observe the testing site for physiologic changes, skin changes or other adverse events daily. Subjects will be provided with a daily diary to record and monitor any observed changes. The daily diary is provided in Appendix 14.3. They will be instructed to notify the investigator of any sudden changes in skin appearance or increase in their arthritic symptoms that are more than minimally tolerated.

Physician Skin Monitoring: At baseline and at every subsequent visit, the investigator will assess the CBD cream site for adverse events. A score will be given corresponding to the assessment tool below:

Score	Definition
0	No erythema
1	Minimal erythema
2	Moderate erythema with sharply defined borders
3	Intense erythema with or without edema
4	Intense erythema with edema and blistering/erosion

- NOTE: Changes in skin appearance will be evaluated using the standardized skin assessment tool above. A patient will be removed from study with a score ≥ 2 .

Clinical Evaluations: Subjects will be monitored weekly for the following:

- Vital sign assessments (i.e., heart rate and blood pressure)
- Suicidal behavior and thoughts as a specific question using the Columbia-Suicide Severity Rating Scale (C-SSRS). The full questionnaire is provided in Attachment 3 (Appendix 14.4).
 - Monitor for somnolence and sedation and advise patients not to drive or operate machinery until they have gained sufficient experience on study drug. Subjects will be asked if they feel more, less, or no change in their level of fatigue during the time they were administering study drug.

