14.3 Daily Sin Monitoring Diary

Day X	Time of onset	Time of symptom improvement	Time of symptom resolution
Itching			
Redness			
Red bumps/hives			
Swelling			
Diarrhea			
Nausea			
Change in appetite			
Fatigue			
Other concerning signs/symptoms			

Signature:

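### Section 6.2 has no exclusion for known hypersensitivity to the creams' components; the clear gap is a known past reaction to shea butter, which is in both creams (minor)

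*Combined protocol and SAP*

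**What the plan says.** Section 6.1 lists six inclusion criteria and section 6.2 fifteen exclusions. None mentions allergy, hypersensitivity or an earlier reaction to anything in the creams. Two exclusions come close:

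- Exclusion 12: "Any skin disease or condition, including eczema, psoriasis, melanoma, acne or contact dermatitis, scarring, imperfections, lesions, tattoos or discoloration that may affect treatment application". The sentence goes on to add effects on site assessment and on absorption.
- Exclusion 8: "Pre-existing CBD or hemp based product usage".

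Section 7.1 describes the active cream as "99.99% pure cannabidiol (CBD) with 100% Pure USDA Organic Shea Butter" and the comparator as "Control – 100% Pure USDA Organic Shea Butter".

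On risk, section 3.1.1 says "Another theoretical risk is contact dermatitis". The daily diary in section 14.3 has rows for itching, redness, swelling and "Red bumps/hives". The medical history in section 9.2 names mental illness, substance abuse and use of hemp products, then leaves room for other relevant history. Allergy is not named.

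On what follows a reaction, section 9.2 says "A patient will be removed from study with a score" of 2 or more, and section 5.1 says "If mild to severe drug-related adverse events are noticed, the creams will be removed immediately". Section 8.3 equates stopping treatment with leaving the study. Section 8.2 does not replace subjects who leave after receiving the cream.

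**The concern.** The plan looks daily for allergic skin reactions after dosing but does not ask about known allergy before dosing. For shea butter this matters more than in a usual two-arm trial. Both conditions contain it, so a subject allergic to it has no unexposed period.

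The first stake is an exposure that one screening question could prevent. The second is the skin-safety endpoint. A reaction to the shared vehicle says nothing about CBD, but it is recorded under whichever cream is in use. A subject removed for it in period 1 never reaches the other cream, so that subject gives no within-subject comparison, and section 11 has no rule for incomplete pairs.

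**Working it through.** **1. Who is still eligible?** Take a person with clear skin and a known past reaction to one component.

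| Component | Where it is used (7.1) | Criterion that could exclude | Result |
|---|---|---|---|
| CBD or hemp | CBD cream only | Exclusion 8 (prior product use); exclusion 12 in part | Mostly excluded, since knowing of a reaction usually implies earlier use |
| Shea butter | Both creams | Exclusion 12 only, if the history is read as a condition affecting application, assessment or absorption | Eligible as written if the skin is clear |

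"Mostly" for CBD and hemp takes exclusion 8 to mean any earlier use; the criterion gives no look-back period.

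**2. The plan's sample size.** Inputs from sections 11.1 and 11.2: significance level 0.05, power 80%, variance 0.25 (SD 0.5), and a 50% reduction. Two assumptions are needed: the reduction is read as a difference δ = 0.5, and the test as two-sided.

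- n = 2(1.960 + 0.842)² × 0.25 / 0.5² = 15.70, rounded up to 16. The stated minimum of 16 reproduces.
- A paired formula with independent periods gives the same number, because the variance of the difference is 2 × 0.25 = 0.5. The text does not say whether 16 means pairs, per arm or in total.

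**3. Power when pairs are lost.** With SD of the difference √0.5 = 0.707, δ/SD = 0.707 and power = Φ(0.707√n − 1.960). This is a normal approximation; the plan names the Wilcoxon signed-rank test.

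| Pairs | 0.707√n − 1.960 | Power |
|---|---|---|
| 40 | 4.472 − 1.960 = 2.512 | 99.4% |
| 38 | 4.359 − 1.960 = 2.399 | 99.2% |
| 36 | 4.243 − 1.960 = 2.283 | 98.9% |
| 32 | 4.000 − 1.960 = 2.040 | 97.9% |

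The documents give no reaction rate. Assumed losses to skin reactions of 1%, 2%, 5% and 10% of 40 are 0.4, 0.8, 2 and 4 subjects. Four losses cost about half a percentage point.

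**4. The less favourable reading.** If 16 means per arm, 32 are needed and 40 − 32 = 8 can be lost. The binomial chance of losing more than 8 of 40 is 0.01% at a 5% loss and 1.5% at 10%. It reaches 41% only at 20%. Compared as two groups, 20 per arm gives 88.5% and 19 per arm 86.9%.

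**5. Direction of any effect on the skin comparison.** Order is randomised 1:1 and both creams contain shea butter. A subject who reacts at first exposure is therefore equally likely to be on either cream, so there is no expected bias. There is noise. With 20 subjects per sequence, one period-1 reaction is 1/20 = 5 percentage points for that cream. Two such reactors start on the same cream with probability 2 × (20/40) × (19/39) = 0.49.

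**The case against.** The strongest case against the point is that cover already exists. Exclusion 12 opens broadly, names contact dermatitis and reaches conditions that affect site assessment; a clinician could read a known contact allergy to the vehicle into it. Exclusion 8 deals with most CBD and hemp reactions. Section 7.5 has the treating physician verify eligibility, and section 9.2 leaves room for other relevant history. After dosing there are a daily diary, skin scoring at visits and an instruction to report sudden changes. Contact dermatitis is called theoretical, and no allergy rate is given. Loss without replacement applies to every dropout, not only to this one.

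Most of this stands. It narrows the gap to shea butter and keeps the severity low. It does not close the gap: exclusion 12 depends on how it is read for someone with clear skin, and the diary and skin scoring detect a reaction but do not prevent it. Consent pages are not part of the reviewed text, so any warning there cannot be judged.

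A reader might infer three stronger things that the documents do not support:

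- That known reactors to either ingredient pass every exclusion. Exclusion 8 contradicts this for most CBD and hemp reactions.
- That the trial loses meaningful power. On the plan's inputs it does not.
- That shea reactions would count against CBD. They would count equally against control when they occur there.

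Nor does every reaction force removal. The skin scale in section 9.2 does so only from a score of 2, while section 5.1 has creams removed for mild drug-related events as well. Those two passages must be reconciled.

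**Conclusion.** The point holds in a limited form and is minor. As written, a person with clear skin and a known shea butter allergy is eligible and would be exposed in both periods, in a protocol that itself names contact dermatitis as a risk. The basis is patient safety, with a secondary gain in a less noisy skin-safety comparison.

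The number of people affected is unknown. The statement that power is barely touched rests on reading the 50% reduction as 0.5, on independent periods with variance 0.25 each, and on assumed losses of up to 10%. The absence of bias rests on the 1:1 randomised order and the shared vehicle.

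**What to change.** Add one exclusion to section 6.2: *Known hypersensitivity or prior allergic reaction to shea butter, cannabis/hemp, cannabidiol or any component of either cream.* Naming all components also covers the few CBD or hemp reactions that exclusion 8 may miss.

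Add the matching question to the medical history under section 9.2 and to its case report form, so that the answer is recorded before randomisation.

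The cost is one line, one question and an occasional extra screen failure. Dose, schedule, endpoints and analysis do not change.

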8.2 Participant Discontinuation/Withdrawal

Participants are free to withdraw from participation in the study at any time upon request.

A participant's study treatment would be discontinued for the following reasons:

- Significant study intervention non-compliance
- If any clinical adverse event (AE), laboratory abnormality, or other medical condition or situation occurs such that continued participation in the study would not be in the best interest of the participant
- Disease progression which requires discontinuation of the study intervention
- If the participant meets an exclusion criterion (either newly developed or not previously recognized) that precludes further study participation
- Participant decision to withdraw from study treatment and/or the study.

The reason for participant discontinuation or withdrawal from study treatment will be recorded. Participants who sign the informed consent form and are randomized but do not receive the study intervention may be replaced. Participants who sign the informed consent form, and are randomized and receive the study intervention, and subsequently withdraw, or are withdrawn or discontinued from the study, will not be replaced.

Participants that withdraw from the study (not only from study treatment, but all study follow-up) will not be contacted for any further study visits.

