14.2 Protocol Amendment History

Version	Date	Description of Change	Brief Rationale
02	11/23/19	Addition of PI address and CRC contact information	Protocol clarification
02	11/23/19	Addition of relevant abbreviations	Protocol clarification
02	11/23/19	Clarification and addition of secondary safety endpoints	FDA Clinical Hold response
02	11/23/19	Addition of one-week follow-up visit	FDA Clinical Hold response
02	11/23/19	Corrected literature references	Protocol clarification
02	11/23/19	Duration of subject participation changed to up to seven (7) weeks	FDA Clinical Hold response
02	11/23/19	Clarified study schema	FDA Clinical Hold response
02	11/23/19	Added “There has yet to be a randomized controlled trial demonstrating benefit of topical CBD products in this patient population. The risks involved as detailed above are mitigated by safety monitoring and are outweighed by the ability to add to the current research in Cannabidiol products, which are currently understudied.”	Added risk/benefit analysis.
02	11/23/19	Added inclusion/exclusion criteria.	FDA Clinical Hold response
02	11/23/19	Clarified product packaging information.	Protocol clarification
02	11/23/19	Added Physician Skin Monitoring Scale	FDA response
02	11/23/19	Clarified clinical blood labs drawn	FDA Clinical Hold Response
02	11/23/19	Relevant changes made to Schedule of Activities	FDA Clinical Hold Response
03	04/27/20	Addition of relevant abbreviations	Protocol clarification
03	04/27/20	Dosage increase from once to BID	Literature review
03	04/27/20	Added change from baseline to endpoints	Protocol clarification
03	04/27/20	Added additional information and references to Background section	Literature review

03	04/27/20	Removed “oil” throughout	Protocol clarification
03	04/27/20	Additional information provided in Section 5.2 Justification for Dose	Information added to support dosage increase
03	04/27/20	Added “Subject is blind” to Section 6.2 Exclusion Criteria	Protocol clarification
03	04/27/20	Added medication examples for Exclusion criteria #15.	Protocol clarification
03	04/27/20	Addition of Section 6.4 Lifestyle Considerations	Protocol clarification
03	04/27/20	Section 7.2 Dosing and Administration – changed dosing to BID. Investigational product is given in three 10mL syringes.	Information changed to support dosage increase
03	04/27/20	Provided list of attachments	Protocol clarification

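### Exclusion 15 bars CYP substrates, but its bracketed names do not fit that word, so the drug-interaction screen has two readings that can admit different patients

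*Combined protocol and SAP*

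**What the plan says.** Section 3.1.1 names the interaction risk: "Exogenous CBD may affect the metabolism of Coumadin and other drugs based on the P450 metabolism". Two exclusions in Section 6.2 bear on it.

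- Exclusion 4 is, in full, "Coumadin use at time of screening".
- Exclusion 15 begins "Subjects taking prescription or non-prescription medication which are substrates of CYP3A4 (Itraconazole, Ketoconazole, Azamulin, Troleandomycin, Verapamil" and continues with bracketed names for CYP2C19, CYP2C8, CYP2C9, CYP1A2 and CYP2B6. It applies within 14 days of a study procedure that it does not identify. The CYP1A2 bracket includes "Phenytoin, Rifampin, Ritonavir, smoking, Teriflunomide, Ciprofloxacin, oral contraceptives".

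The criterion itself does not say whether the names are illustrative or exhaustive. The amendment history (Section 14.2, version 03) describes the change as "Added medication examples for Exclusion criteria #15".

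Inclusion 4, Exclusion 11 and Section 6.4 all count hormonal contraception as an acceptable method. Section 7.6 requires concomitant medication to be reported in the case report form and prohibits none. Section 8.2 discontinues treatment "If the participant meets an exclusion criterion (either newly developed or not previously recognized) that precludes further study participation", and separately when an adverse event, laboratory abnormality or other situation makes continuing contrary to the participant's best interest.

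**The concern.** An eligibility rule should give the same answer whoever applies it. Here the class word and the names point to different patients. A screener who works from the word turns away anyone on a drug cleared by one of six enzymes. A screener who works from the list turns away smokers and oral contraceptive users, and may admit someone on a substrate that is not named.

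The stakes are safety screening and description of the population. For the other drugs in Section 3.1.1, Exclusion 15 is the only specific check at entry. Section 6.3 also asks for screen-failure details to be kept for CONSORT reporting. A count of failures under Exclusion 15 cannot be interpreted if two rules were in use.

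**Working it through.** No figure in the plan depends on this point, so the check is a count and a comparison of sections.

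**Count of bracketed entries in Exclusion 15**

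| Enzyme | Entries |
|---|---|
| CYP3A4 | 7 |
| CYP2C19 | 4 |
| CYP2C8 | 5 |
| CYP2C9 | 6 |
| CYP1A2 | 10 |
| CYP2B6 | 8 |

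Total: 7 + 4 + 5 + 6 + 10 + 8 = 40. Rifampin appears four times, ticlopidine twice and carbamazepine twice, so the distinct entries number 40 − 3 − 1 − 1 = 35. Coumadin is not among them.

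**Direction of the risk.** Section 3.1.1 describes CBD acting on the metabolism of other drugs. The drugs exposed to that risk are the ones the enzymes metabolise, that is, substrates. The class word in Exclusion 15 therefore matches the stated risk.

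**Fit of the names to the word.** Two entries can be judged from the documents alone. Smoking is not a medication, so it falls outside the criterion's own wording. Oral contraceptives are barred by the list, while three other places accept hormonal contraception without excepting the oral form. That is 2 of 35 distinct entries. The documents assign no role to any entry and never use the words inhibitor or inducer. By general pharmacology, many other entries (ketoconazole, rifampin and fluconazole, for example) are known mainly as inhibitors or inducers, though some (verapamil, omeprazole, celecoxib, bupropion) are also substrates. I treat this as background and do not count it.

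**The two readings applied to the same patient**

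| Patient | Class word as the rule | List as the rule |
|---|---|---|
| Smoker on no medication | Not excluded | Excluded |
| Oral contraceptive user | Depends on whether the product is a substrate; not stated | Excluded, although Inclusion 4 accepts hormonal methods |
| Patient on an unlisted substrate | Excluded | Not excluded |

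The first and third rows give opposite decisions. The third row is the one that matters for Section 3.1.1.

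**Timing.** Exclusion 4 is tied to the time of screening; Exclusion 15 has a 14-day window. The nominal interval from screening (Day −7) to the end of the second period (Day 28) is 28 − (−7) = 35 days. If Coumadin is started in that interval, Section 7.6 leads only to its being recorded. Whether the newly-developed clause of Section 8.2 applies is unclear: a criterion defined at screening may not be capable of developing later, and the clause adds a further condition that the criterion must preclude participation. The best-interest clause of Section 8.2 remains available throughout.

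**The case against.** The best defence is that the amendment log settles the matter: the names are examples, the word is the rule, and the word covers the class at risk. On that reading the screen exists and only its illustrations are poor. Much of this stands. The defect is ambiguity in application, not a missing rule. It does not remove the problem, because nothing in Exclusion 15 tells a screener that the list is illustrative, and at least one example cannot illustrate the word.

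A reader might infer several stronger points that the documents do not support.

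- *That the list is mostly inhibitors and inducers.* This is outside knowledge. Nor does the repetition of rifampin help, since nothing in the text stops one drug from being a substrate of several enzymes.
- *That Coumadin is left uncovered.* Exclusion 4 screens it by name, the word substrates may reach it as well, and the best-interest clause of Section 8.2 applies on study. Its absence from a list of examples proves nothing.
- *That recruitment suffers by a known amount.* The documents give no data on medication use among these patients, so no number follows.
- *That the treatment comparison is biased.* Section 11.1 plans a within-subject analysis, and stable background medication is largely shared by a patient's two periods. No bias is shown.

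**Conclusion.** The point holds as an internal inconsistency in a safety eligibility rule. Exclusion 15 has a class word that fits Section 3.1.1 and names that do not all fit the word, and the two readings can admit different patients. From the text alone, one entry (smoking) lies outside the criterion's own terms and one (oral contraceptives) conflicts with Inclusion 4, Exclusion 11 and Section 6.4. The contraceptive conflict assumes that hormonal contraception includes oral products, which no section denies.

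The screening ambiguity is confined to drugs other than Coumadin. For Coumadin the open question is narrower: which clause of Section 8.2 governs a start after screening. The number of patients affected cannot be derived, and no effect on power or on the treatment estimate is claimed. The point is worth correcting because the rule is the only specific entry screen for a risk that the protocol itself states.

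**What to change.** Amend the wording in three places, leaving every clinical choice to the sponsor.

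1. Reconcile Exclusion 15 with Section 3.1.1. State which direction of interaction it is meant to prevent (CBD acting on other drugs, other drugs acting on CBD, or both), make the class word and the names agree, and say within the criterion whether the names are examples or a complete list.
2. Reconcile the oral contraceptive entry with Inclusion 4, Exclusion 11 and Section 6.4.
3. Reconcile the timing of Exclusions 4 and 15 with Section 8.2. Identify the study procedure to which the 14 days refer, and say how Section 8.2 treats a drug named in either exclusion that is started after screening.

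The cost is protocol text and a checked drug list. No visits, assessments or data are added, and the analysis does not change.
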